2 ELIGIBILITY ASSESSMENT AND ENROLLMENT

2.1 ELIGIBILITY CRITERIA

2.1.1 Inclusion Criteria

- 2.1.1.1 Moderate or severe cGVHD (after allogeneic hematopoietic stem cell transplantation) diagnosed and staged per NIH criteria,⁴ **Appendix B** and **Appendix C**. Responses to JAK inhibitors have not been restricted to specific organs, so any organ involvement is eligible.
- 2.1.1.2 Age \geq 18 years of age. Because inadequate dosing or adverse event data are currently available on the use of baricitinib in patients <18 years of age, children are excluded from this study.
- 2.1.1.3 Karnofsky performance score \geq 50% (**Appendix A**)
- 2.1.1.4 Chronic GVHD that did not respond to high-dose corticosteroids (prednisone at 1.0 mg/kg/day for at least 1 week or prednisone at 0.5 mg/kg/day or 1 mg/kg every other day for at least 4 weeks), or second-line therapy (any)
- 2.1.1.5 If patient is taking systemic therapy for cGVHD at the time of enrollment, they must be on a stable or tapering doses in the preceding 4 weeks.
- 2.1.1.6 Patients must have normal organ and marrow function as defined below:
 - absolute neutrophil count \geq 1,000/mcL
 - absolute lymphocyte count \geq 500/mcL
 - platelets \geq 50,000/mcL
 - hemoglobin \geq 9 g/dL
 - total bilirubin \leq 1.5 X institutional upper limit of normal, unless there is a known history of Gilbert's disease
 - AST(SGOT)/ALT(SGPT) \leq 3 X institutional upper limit of normal
 - Creatinine < 1.5 times the upper limit of normal, **or:**
 - creatinine clearance \geq 50 mL/min/1.73 m². Creatinine clearance should be calculated per institutional standard.
- 2.1.1.7 Primary malignancy for which the patient received transplant has been stable for 3 months prior to enrollment on study
- 2.1.1.8 The effects of baricitinib on human fetal development are unknown. Women of child-bearing potential and men must agree to use 2 effective forms of contraception (hormonal or barrier method of birth control; abstinence) for the duration of study participation and for at least 7 days after study drug exposure. Should a woman become

pregnant or suspect she is pregnant while she or her partner is participating in this study, or if a man's partner becomes pregnant or suspects she is pregnant while he is participating in this study, she or he should inform their treating physician immediately.

- 2.1.1.9 Ability of subject to understand and the willingness to sign a written informed consent document.

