Neutrophils $< 1.0 \times 10^9/L$, platelets $< 50 \times 10^9/L$, creatinine ≥ 1.5 times the upper limit of normal **or** estimated creatinine clearance $< 50 \text{ mL/min/1.73m}^2$ (Cockcroft-Gault formula), serum aspartate aminotransferase or alanine aminotransferase concentration $> 3 \times \text{ULN}$ or total bilirubin $\geq 1.5 \times \text{ULN}$

Progressive malignancy, uncontrolled infection or any major organ dysfunction as defined by the protocol

Design:

This is a Phase 1/2 trial to determine the safety and efficacy of baricitinib in patients with cGVHD that is refractory to steroids.

Patients will initially be treated with baricitinib at 2mg daily for 12 weeks. If the response at 12 weeks is a CR and there has not been a DLT, the dose will remain at 2mg daily for an additional 12 weeks, with the primary response assessment at 24 weeks of total treatment. If the response is a PR or stable disease, the dose will be increased to 4mg daily for an additional 12 weeks, with the primary response assessment at 24 weeks of total treatment. If there is progression of disease at any time within the first 12 weeks, the dose can be increased to 4mg daily at that time, and patients will continue for a total of 24 weeks of treatment. Patients will have the option to continue baricitinib for an additional 6 months as tolerated if they have stable or responding disease.

The co-primary endpoint of safety will be determined by rate, severity, and duration of adverse events based on CTCAE v4 criteria. Assessment for DLTs will occur every 2 weeks during the first 4 weeks of each dose level. Safety monitoring will occur every 4 weeks thereafter.

The co-primary endpoint of efficacy will be defined as rate of overall response at 24 weeks per NIH consensus criteria (CR or PR).

Peripheral blood samples will be collected prior to treatment, at 2 weeks, at 12 weeks and every 12 weeks thereafter to evaluate cytokine and cellular profiles, STAT phosphorylation, candidate chronic GVHD biomarkers. Pharmacokinetic studies will also be performed at each dose level.

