1.2.3 Baricitinib

Baricitinib (LY3009104, formerly INCB028050, Eli Lilly and Company) is a selective JAK1/2 inhibitor that has been studied in patients with inflammatory conditions such as rheumatoid arthritis, psoriasis, and diabetic nephropathy. It is an oral, potent, and reversible inhibitor of JAK1 (IC₅₀=5.9 nM) and JAK2 (IC₅₀=5.7 nM), with less potency for JAK3, tyrosine kinase 2 (TYK2), or other kinases.⁴⁵ In addition, it has demonstrated excellent potency for inhibition of IL-2-, IL-6-, and IL-23- stimulated phosphorylation of JAKs and STATs, and IL-2 induced proliferation of T-cells. In preclinical models of arthritis, it has demonstrated anti-inflammatory effects while preserving humoral immunity and had no hematologic effects.⁴⁵ It has been tested in doses of 0.5mg-20mg in over 3000 patients and healthy volunteers, and the safety profile is well understood.^{46,47} Phase 1, 2, and 3 studies in RA have been completed, and several studies in patients with psoriasis and diabetic nephropathy are ongoing. Common toxicities seen across studies include decreases in hemoglobin and neutrophils (mean values usually remaining within the normal range), increases in platelets (mean values usually remaining within the normal range), increases in creatinine (mean values usually remaining within the normal range) and increases in exposure in patients with renal impairment, increases in total cholesterol, high-density lipoprotein (HDL), low-density lipoprotein (LDL), and triglycerides, increases in hepatic enzymes, increases in creatine phosphokinase (CPK), and increased incidence of infections (mostly respiratory). Decreases in neutrophils and hemoglobin and other lab abnormalities have been reversible upon discontinuation of the drug.

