12 HUMAN SUBJECTS PROTECTIONS

12.1 RATIONALE FOR SUBJECT SELECTION

No subjects will be excluded from participation based on gender, race or ethnicity. The study will be open to all subjects who satisfy the inclusion criteria and provide an informed consent to the protocol.

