14.1.2 Toxicity

As of August 2021, approximately 13,800 subjects have received baricitinib since the start of clinical development program.

A large, randomized trial of tofacitinib (a JAK 1/2/3 inhibitor) in patients with rheumatoid arthritis detected higher risk of heart attack, stroke, cancer and blood clots and death when compared to standard therapy with anti-TNF drugs. Based on these studies in September 2021, FDA extended this warning to baricitinib (JAK 1/2) and another JAK inhibitor drug used in arthritis. This warning has not been extended to similar drugs used for cancer (or GVHD).

The following potential treatment related side effects have been identified:

Increased Adverse Events Due to Increased Exposures in Patients with Renal Impairment:

Data from completed studies indicate that subjects with renal impairment have increased exposures to baricitinib. Increased exposure could place a person at increased risk for any other risk that is related to exposure. Therefore, adjustment in dose has been implemented in clinical studies to compensate for these observed differences. Investigators should follow dosing guidelines specified in the protocol, and monitor creatinine in study subjects and follow protocol drug interruption and discontinuation criteria.

Blood Clots in the Blood Vessels

Increased incidence of pulmonary embolism, venous and arterial thrombosis with another JAK inhibitor vs. TNF blockers. Events of deep venous thrombosis (DVT) and pulmonary embolism (PE) have been reported in patients receiving baricitinib.

Data from the placebo-controlled time period from the integrated safety analysis of Phase 2/3 RA studies showed a numerical imbalance in the reports of DVT/PE, with more events reported in the baricitinib 4-mg group compared to the placebo group. The exposure-adjusted incidence rate (EAIR) of DVT/PE for baricitinib-treated RA patients over long-term exposures [0.45] was similar to the background rates published in the literature. There was no pattern of increased or decreased risk in any given 48-week time period including long-term exposures. Risk factors found more commonly in patients with these events included prior history of DVT/PE, obesity, and older age. In a retrospective observational study of baricitinib in RA patients, a higher incidence rate of venous thromboembolic events was observed compared to patients treated with TNF blockers.

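### The renal entry rule contradicts itself: the Précis requires both kidney tests to be passed, Section 2.1.1.6 only one, and no renal dose step backs it up

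*Combined protocol and SAP*

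**What the plan says.** - **Précis, Exclusion.** The renal exclusion reads "creatinine ≥ 1.5 times the upper limit of normal or estimated creatinine clearance" below 50 mL/min/1.73 m², with Cockcroft-Gault named as the formula.
- **Section 2.1.1.6.** The list opens with "Patients must have normal organ and marrow function as defined below". The renal entry is "Creatinine < 1.5 times the upper limit of normal, or" a clearance of at least 50 mL/min/1.73 m². On method it says "Creatinine clearance should be calculated per institutional standard".
- **Section 2.1.2.** No exclusion sets a clearance or creatinine limit. Criterion 2.1.2.3 excludes serious medical conditions in the previous 4 weeks that create unacceptable risk or confound interpretation, and names acute kidney injury as one example.
- **Sections 1.2.3 and 14.1.2.** The known effects of the drug include "increases in exposure in patients with renal impairment". Section 14.1.2 adds: "Increased exposure could place a person at increased risk for any other risk that is related to exposure". It continues: "Therefore, adjustment in dose has been implemented in clinical studies to compensate for these observed differences". Investigators are then referred to the dosing guidelines in the protocol.
- **Sections 3.1 to 3.3.** Cohort 1 starts at 2 mg daily. The dose rises to 4 mg at 12 weeks for partial response or unchanged disease, and may rise earlier on progression. Cohort 2, if opened, starts at 4 mg. Reductions follow a DLT or a toxicity, and none depends on renal function.

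**The concern.** An exclusion joined by 'or' becomes an inclusion joined by 'and'. Here the 'or' appears in both forms, so the two statements define different populations. Staff who screen from the Précis and staff who screen from the numbered list would decide differently on the same patient.

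The disagreement concerns a drug whose exposure, by the protocol's own account, rises as renal function falls. Because Section 3 has no renal dose step, the entry limit is the only fixed control on low clearance before the first dose. At stake is whether patients with clearance below 50 receive 2 mg, and later perhaps 4 mg, on the same schedule as everyone else.

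**Working it through.** **Step 1. Logic.** Let A be creatinine below 1.5 × ULN and B be clearance of at least 50. The Précis excludes (not A) or (not B), so it admits A and B. Section 2.1.1.6 admits A or B.

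| Creatinine < 1.5 × ULN | Clearance ≥ 50 | Section 2.1.1.6 | Précis |
|---|---|---|---|
| yes | yes | meets | not excluded |
| yes | no | meets | excluded |
| no | yes | meets | excluded |
| no | no | fails | excluded |

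The rules disagree in 2 of 4 cells. The second row carries the exposure concern. With 'and' in 2.1.1.6, all four rows agree.

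**Step 2. Does another rule close the second row?** Section 2.1.2 has no renal threshold. Criterion 2.1.2.3 depends on judgement and has no cutoff, so it need not catch stable low clearance. In Sections 3.1 to 3.3 the 1 mg level is reached only after a DLT or toxicity. The pharmacokinetic samples in Section 5.1.3 are meant to check exposure, but they are batch tested up to two years after collection and no rule links a result to a dose.

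**Step 3. Can the second row be occupied?** The documents give no creatinine, age or weight distribution, so this is an illustration on assumed inputs: ULN 1.0 to 1.1 mg/dL for women and 1.2 to 1.3 for men, with the ages, weights and body surface areas (BSA) shown.

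Raw Cockcroft-Gault = (140 − age) × kg / (72 × creatinine), × 0.85 for women. Indexed = raw × 1.73 / BSA. Example, woman with ULN 1.0 and creatinine at 1.0 × ULN: 80 × 60 × 0.85 / 72 = 56.7 raw; 56.7 × 1.73 / 1.6 = 61.3 indexed. The creatinine multiple at which clearance equals 50 is the value at 1.0 × ULN divided by 50.

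| Assumed patient | Raw at 1.0 × ULN | Indexed at 1.0 × ULN | Multiple for 50, raw | Multiple for 50, indexed |
|---|---|---|---|---|
| Woman 60 y, 60 kg, 1.6 m² | 51.5–56.7 | 55.7–61.3 | 1.03–1.13 | 1.11–1.23 |
| Man 70 y, 70 kg, 1.8 m² | 52.4–56.7 | 50.3–54.5 | 1.05–1.13 | 1.01–1.09 |
| Man 50 y, 80 kg, 2.0 m² | 76.9–83.3 | 66.5–72.1 | 1.54–1.67 | 1.33–1.44 |
| Man 40 y, 100 kg, 2.2 m² | 106.8–115.7 | 84.0–91.0 | 2.14–2.31 | 1.68–1.82 |

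The first two patients can fall below 50 while passing the creatinine test under either convention. The third can do so only if clearance is indexed, which shows why the method must be stated. The fourth cannot. He shows that the third row of the logic table is also real: at 1.5 × ULN his clearance is 56.0–60.7 indexed (84.0/1.5 and 91.0/1.5) or 71.2–77.2 raw.

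**Step 4. Accrual cost.** Section 10 expects 8 to 12 patients a year, so one lost candidate costs 12/12 = 1.0 to 12/8 = 1.5 months.

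**The case against.** **The Précis is part of the same protocol.** It expressly excludes the patient in question, so the documents conflict rather than plainly admit that patient. This stands. A reader might use Section 12.1 to give the numbered list priority, since it says "The study will be open to all subjects who satisfy the inclusion criteria". But that sentence belongs to a statement about fair selection by gender, race and ethnicity. It sets no precedence between texts, and read literally it would also override the exclusions in 2.1.2.

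**The Précis may be the text in error.** Section 2.1.1.6 differs from it elsewhere: it adds lymphocyte and hemoglobin limits and an exception for Gilbert's disease. The documents do not show which renal rule was intended. Either way one text must change. If 'or' was meant, the protocol admits low clearance without the dose adjustment that Section 14.1.2 says was used in other studies.

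**A reader might conclude that anyone with creatinine below 1.5 × ULN is eligible at any clearance.** That goes too far, because 2.1.2.3 lets an investigator exclude marked renal impairment. It mitigates the gap without setting a limit.

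**The link to harm is thin.** No section says at what clearance exposure rises, by how much, or where other studies adjusted the dose. Doses of 0.5 to 20 mg have been studied, mostly in other populations. The excess hematologic toxicity in Section 1.2.3 was at 8 mg, twice the maximum here. In cohort 1, 4 mg normally follows 12 weeks at 2 mg. A 4 mg start requires no response among the first 7 patients and no safety issue. Chemistry is drawn about every two weeks through week 12, and NSAIDs are prohibited. All of this stands and limits the claim about consequences, but it leaves the contradiction untouched.

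**Conclusion.** The contradiction is certain from the text: the two renal rules disagree in 2 of 4 combinations and name different clearance methods. Under the numbered criterion, a patient with creatinine below 1.5 × ULN and clearance below 50 meets the renal requirement. No other numbered criterion sets a clearance cutoff, and no dose rule responds to renal function. This should be fixed.

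The consequence is less certain. The number of affected patients and the size of the exposure increase cannot be derived from the documents, so the safety effect is plausible but unquantified. The clearance figures rest on assumed ULN, age, weight and body surface area and show only that such patients can exist; the finding does not depend on them. A reader might go on to infer that dose reduction is needed just below 50, or that efficacy power or the DLT stopping rule is compromised. The documents support neither inference.

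**What to change.** In 2.1.1.6 change 'or' to 'and', so that a clearance of at least 50 is required of every patient, as in the Précis. State one method in both places: Cockcroft-Gault, saying explicitly whether and how it is indexed to 1.73 m². The formula contains no body surface area, although both limits are expressed per 1.73 m².

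This is a one-line edit plus matching wording on method. No new test is needed, because Section 2.2 already lists creatinine clearance at screening. Two groups that the numbered criterion now admits become ineligible: candidates with clearance below 50, and candidates with creatinine of at least 1.5 × ULN but clearance of at least 50. How many is unknown; each costs about 1 to 1.5 months of accrual. The change governs entry only and does not address clearance that falls during treatment.

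If the sponsor did intend the looser rule, the Précis should be corrected instead and a renal dose step added to Section 3.

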2.1.2 Exclusion Criteria

- 2.1.2.1 Systemic immune suppression or systemic therapy for cGVHD started within preceding 4 weeks.
- 2.1.2.2 Hypersensitivity to JAK inhibitors
- 2.1.2.3 Any serious medical condition within the previous 4 weeks which places the subject at an unacceptable risk if he or she were to participate in the study or confounds the ability to interpret data from the study, including, but not limited to, symptomatic congestive heart failure, unstable angina pectoris, uncontrolled cardiac arrhythmias, acute kidney injury, or psychiatric illness/social situations that would limit compliance with study requirements.
- 2.1.2.4 Uncontrolled infection, including active HIV-1, Hepatitis B (HBV) and/or Hepatitis C (HCV) infection (positive HBV or HCV viral load in the setting of positive HBV core antibody or surface antibody or HCV antibody). History of HBV or HCV is allowed if there is no uncontrolled viral infection. Because the study agent may impact response to infections, patients with any active viral infection are excluded.
- 2.1.2.5 Recurrent or progressive malignancy requiring anticancer treatment
- 2.1.2.6 Other cancer except that for which the transplant was done <2 years before study entry, except non-melanoma skin cancer or carcinoma in situ of the uterine cervix or breast
- 2.1.2.7 Patients who are receiving any other investigational agents
- 2.1.2.8 NIH lung score 3 ([Appendix D](#))
- 2.1.2.9 Pregnant women are excluded from this study because the teratogenic effects of baricitinib are unknown. Because there is an unknown but potential risk for adverse events in nursing infants secondary to treatment of the mother with baricitinib, breastfeeding should be discontinued if the mother is treated with this agent.

2.1.3 Recruitment Strategies

This protocol may be abstracted into a plain language announcement posted on NIH websites and on NIH social media platforms. In addition, patients will be directly referred to the NIH for this clinical trial through the well-developed NIH chronic GVHD study group referral base. In addition, patients who are referred for the CCR protocol "Natural History Study of Clinical and Biological Factors Determining Outcomes in Chronic Graft-Versus-Host Disease" study (04-C-0281) will be screened for this trial. Also, patients who undergo SCT at the NIH will be eligible for enrollment on this trial, which will provide another mechanism for screening patients. Finally, physicians and patients will be made aware of the study through our patient advocacy groups (National Marrow Donor Program, National Bone Marrow Transplant Link, Blood & Marrow Transplant Information Network, Meredith Cowden Foundation) and other professional forums.

2.2 SCREENING EVALUATION

Screening procedures will be performed on a CCR screening protocol (01C0129), or most commonly on 04C0281 “Natural History of Chronic GVHD.” All studies must be completed within 4 weeks prior to enrollment:

- History and physical exam, Karnofsky performance score
- Documentation of cGVHD diagnosis, NIH organ and global severity stage
- Laboratory studies: CBC, platelets, differential, PT/PTT, serum chemistries (including sodium, potassium, chloride, CO₂, calcium, magnesium, phosphorus, blood urea nitrogen [BUN], creatinine/creatinine clearance, glucose, albumin, total protein, alkaline phosphatase, total bilirubin, AST [SGOT], ALT [SGPT], lactate dehydrogenase [LDH], and uric acid), creatine kinase (CK), urinalysis, pregnancy testing (in women of childbearing potential), thyroid-stimulating hormone (TSH), free T4
- Additional screening studies: Serologies for HIV, HBV, HCV; CMV PCR; blood and urine cultures, respiratory viral panel. Cultures with no growth present at 48 hours will be deemed negative.
- Pulmonary function tests (PFTs): FEV1, FEV1/FVC ratio, RV, RV/TLC, FEF25-75, DLCO; this will include pre- and post-bronchodilator evaluation
- Chest CT scan in inspiration and end-expiration
- Electrocardiogram (ECG) and echocardiogram

For baseline evaluations, please see Section 2.4.

2.3 PARTICIPANT REGISTRATION AND STATUS UPDATE PROCEDURES

Registration and status updates (e.g., when a participant is taken off protocol therapy and when a participant is taken off-study) will take place per CCR SOP ADCR-2, CCR Participant Registration & Status Updates found at:

<https://ccrod.cancer.gov/confluence/pages/viewpage.action?pageId=73203825>.

2.3.1 Treatment Assignment and Randomization Procedures

Cohorts

Number	Name	Description
1	Phase I cohort	Patients who have undergone hematopoietic allogeneic transplant and have moderate to severe cGVHD that is refractory to treatment with steroids up to 21 patients, for response assessment at 2-4 mg
2	Phase II cohort	Patients who have undergone hematopoietic allogeneic transplant and have moderate to severe cGVHD that is refractory to treatment with steroids after response determination in cohort 1.

Arms

Number	Name	Description
1	Phase I Arm	Baricitinib 2 mg per day, increasing to 4 mg per day in patients who have a partial response or unchanged disease at 12 weeks
2	Phase II Arm	Baricitinib 4 mg per day

Arm Assignment

Patients in Cohort I will be directly assigned to Arm I. Patients in Cohort II will be directly assigned to Arm II.

2.4 BASELINE EVALUATION

The following studies will be performed at baseline after consent and enrollment on this protocol and within 10 days prior to starting the study drug, unless otherwise indicated below. Tests done at screening that fall within the appropriate timeframe for baseline testing need not be repeated.

- History and physical exam, Karnofsky performance status
- Documentation of cGVHD diagnosis per NIH criteria (ref), NIH organ and global stage ([Appendix D](#) and [Appendix E](#)), baseline assessments (clinician assessment form A and patient assessment form B) ([Appendix F](#) and [Appendix G](#)) per NIH response criteria,⁵¹ date of cGVHD diagnosis, prior and current treatments, prednisone or other steroid dose, and other patient, donor, and transplant characteristics ([Appendix H](#))
- Laboratory studies: CBC with differential, serum chemistries (including sodium, potassium, chloride, CO₂, calcium, magnesium, phosphorus, blood urea nitrogen (BUN), creatinine, glucose, albumin, total protein, alkaline phosphatase, total bilirubin, AST (SGOT), ALT (SGPT), lactate dehydrogenase (LDH), uric acid), CK, urinalysis, pregnancy test, TBNK, drug levels if pertinent (tacrolimus, cyclosporine, sirolimus), CRP, C3 and C4, immunoglobulin levels, CMV PCR, BK virus PCR (blood and urine), fasting lipid panel
- Pregnancy test in women that can have children
- MRI of the involved extremity if clinically indicated (acceptable if done within 4 weeks)
- Specialty evaluations of cGVHD (acceptable within 4 weeks): dermatology, ophthalmology, dental, rehabilitation and occupational therapy, gynecology for females
- Occupational therapy evaluation: functional assessment (ACS and HAQ), fatigue assessment (MDFI), and upper extremity use (DASH/MAM) (See [Appendix L](#))
- Patient-reported outcome surveys: Lee cGVHD symptom scale, human activity profile, FACT-BMT (See [Appendix I](#))
- Optional diagnostic and research biopsies of the skin and mouth, and other organs (only if clinically indicated). Biopsies performed within 3 months prior to enrollment (e.g. on 04-C-0281 “Natural History of Chronic GVHD” protocol) are acceptable. Patients may opt out of research and diagnostic biopsies and these will not be required for initiating study drug.

- Research samples (blood, saliva, oral microbiome swabs) (see Section 5.1) Saliva and oral microbiome swabs will be collected at the time of the oral biopsy, if performed
- Documentation of concurrent medications

Of note: Patients who have already been enrolled, but who have symptoms suggestive of infection (fever, productive cough, radiologic findings) at the baseline evaluation will have further workup as standard of care to rule out active infection. Patients with active infection will be treated until the infection is under control or antibiotic therapy is completed. Baseline procedures that have exceeded the desired timeframe will be repeated before the patient may begin study therapy.

